Apart from the discussion between early or late passive mobilization, there is also no consensus on which rehabilitation programs are better.^{8–10,15,17,26,38} Several studies and systematic reviews have been published on the subject, focusing mainly on the times of progression.^{4,8,40–42,44,45,23,28–30,32,34,37,38} These studies all define a four-stage process consisting of: a) immobilization, b) passive range of motion; c) active range of motion and d) strengthening, with variable times of progression.^{9,15,20,28,33} The total duration of the rehabilitation process is also variable, with some studies stating that it might take up to 6-12 months to regain full strength.^{4,33,35}

Regarding rehabilitation setting, some studies suggest that home-based therapy, based on exercise, could be as effective as clinic-based interventions.^{21,26,46,47} This is in line with the recent trends in healthcare delivery, away from inpatient care and towards home-based care with the intent of improving cost-effectiveness.

Given the high incidence and prevalence of shoulder rotator tears, and the associated morbidity, which represents a huge economic burden^{3,16,48} it is essential to ensure the access to cost-effective rehabilitation.⁴⁷ In this regard, digital health solutions that empower patients, maximize engagement and allow home-based rehabilitation without the need for constant therapist supervision, could improve effectiveness and lower the cost of rehabilitation.

SH-RCT-ARCR-01 Study Protocol

SWORD Health has developed a novel digital biofeedback system for home-based physical rehabilitation (SWORD Phoenix®). Using inertial motion trackers, this system digitizes patient motion and provides real-time feedback on performance through a mobile app. It also includes a web-based platform that allows the clinical team to prescribe, monitor and adapt the rehabilitation process remotely. This way, the system allows patients to perform independent rehabilitation sessions at home without the need for constant therapist supervision, ensuring remote monitoring throughout the rehabilitation program.

2. Study Objective

The objective of the present study is to evaluate the clinical outcomes of a home-based rehabilitation program using this system against conventional home-based rehabilitation after arthroscopic rotator cuff repair. We hypothesize that the clinical outcomes of such a program will be at least similar to those of traditional rehabilitation.

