5.1 Primary outcome

The primary outcome will be the change in patient functional assessment compared to the baseline, measured through the Constant Score.

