5.2 Secondary outcomes

The secondary outcomes will be:

- The change in patient reported function in comparison to the baseline, measured by the QuickDASH score
- The change in shoulder range of motion in comparison to the baseline, measured by the shoulder flexion degree in a sitting position (in degrees)

6. Sample size estimate

Sample size estimation was performed taking into consideration the primary outcome measure – The Constant Score - and a non-inferiority scenario.

In the absence of similar studies, the calculations were made taking into account the study by Arndt *et al.* (2012)⁴⁰. This was a large study (n=100 patients) which compared two different rehabilitation protocols after ARCR and which used the same primary outcome as our study. In this study, the standard deviation of the Constant

Score at baseline was 12.0. A Minimal Clinically Important Difference (MCID) of 10.4 was considered, based on the study by Constant *et al.* (2008).⁵⁵

Considering a power of 90%, a two-sided 0.05 significance level and a 10% dropout rate, 68 patients would be necessary to detect a 10.4 points difference between the two groups.

7. Location of Recruitment

Patients will be recruited at Hospital da Prelada - [name] da Cruz.

8. Inclusion criteria

- a) Patients over 18 and under 70 years old
- b) Shoulder pain and functional limitation with clinical examination compatible with reparable rotator cuff tear
- c) Imaging (MRI or ultrasound) evidence of rotator cuff tear (supra and/or infraspinatus tendon tear inferior to 5cm)
- d) Indication for a rotator cuff repair according to the patient's orthopedic surgeon
- e) Ability to understand simple and complex motor commands
- f) Availability of a carer to assist the patient after surgery

9. Exclusion criteria

Preoperative

- a) Patients with indication for revision cuff repair
- b) Complex cuff tears (involving subscapularis tendon or more than one tendon besides supra and infraspinatus, or massive dimension tears)

- c) Glenohumeral arthritis
- d) Irreparable tendon defect
- e) Patients with concomitant neurological disorders (ex. Stroke, Parkinson's disease, multiple sclerosis)
- f) Aphasia, dementia or psychiatric comorbidity interfering with the communication or compliance to the rehabilitation process
- g) Respiratory, cardiac, metabolic conditions or others incompatible with at least 30 minutes of light to moderate physical activity

Postoperative

- h) Irreparable tendon lesion

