Patients in the active comparator group will receive face-to-face rehabilitation sessions provided by a physical therapist. Therefore, patient safety will be ensured at all times during the sessions. Patients will be able to report adverse events to their physical therapist. Moreover, the patient's orthopedic surgeon will be notified in case of detrimental clinical progression, so that the patient can be re-evaluated.

For patients in the experimental group, safety of the remote sessions will be evaluated through pain and fatigue scores (graduated from 0 to 10) collected at the end of each session. These will be presented to the patient using the mobile App and will be available for remote monitoring by their physical therapist. In case of excessive pain or fatigue, patients will be contacted by their physical therapist to ascertain the cause and change prescription if needed. Patients will also be asked to report any other adverse events to their physical therapist by telephone. Moreover, the patient's orthopedic surgeon will be notified in case of detrimental clinical progression, so that the patient can be re-evaluated.

The adverse events will be registered in the patient's file (beginning date, resolution date (if applicable), resolution state, severity).

16. Statistical analysis

To assess differences in clinical and demographic variables of the patients allocated to the two study groups, independent samples t test or Mann-Whitney U test will be used for quantitative variables. For qualitative variables, Chi-squared test or Fisher's exact test will be used.

Outcome analysis will be performed using a per-protocol analysis. The impact of the interventions in the primary and secondary outcomes will be evaluated considering

the change between baseline and week 20. Differences between the two study groups will be performed using independent samples t test or Mann-Whitney U test.

Since outcomes will be measured in several different times during the rehabilitation program, a repeated measures analysis will also be performed, using a 3x2 ANOVA with group as an independent factor and time as a within-subjects factor.

17. Potential Risks and Benefits to Participants

There are no invasive procedures involved in this research protocol and, given the nature of the intervention, no relevant risks are foreseen.

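### The trial is framed and sized for non-inferiority, but no margin is declared and Section 16 plans only tests of difference, with no rule for concluding non-inferiority

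*Combined protocol and SAP*

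**What the plan says.** - **Section 2 (Study Objective)** hypothesises that "the clinical outcomes of such a program will be at least similar to those of traditional rehabilitation". It attaches no numerical limit.
- **Section 5.1:** "The primary outcome will be the change in patient functional assessment compared to the baseline, measured through the Constant Score". Section 16 fixes the time point as the change from baseline to week 20.
- **Section 6** bases the sample size on the Constant Score "and a non-inferiority scenario". It then states: "A Minimal Clinically Important Difference (MCID) of 10.4 was considered". The SD comes from an earlier randomised trial of two rehabilitation protocols, in which the SD of the Constant "Score at baseline was 12.0". With 90% power, two-sided 0.05 and 10% dropout, it concludes that "68 patients would be necessary to detect a 10.4 points difference between the two groups".
- **Section 16:** "Outcome analysis will be performed using a per-protocol analysis". The group comparison is given as: "Differences between the two study groups will be performed using independent samples t test or Mann-Whitney U test". A repeated-measures ANOVA is added. Nothing else is said about how the primary question will be decided.

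**The concern.** The objective is a non-inferiority objective, but the analysis is a test of the null hypothesis of no difference. Such a test can show that one arm is better. It cannot show that the experimental arm is not worse by more than an acceptable amount.

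The 10.4 points work as an implicit limit in the sizing, but Section 6 calls the figure an MCID and a difference to detect. It is never named as a margin, justified as one, or carried into Section 16. If the Mann-Whitney test is chosen, its p-value alone gives no effect in Constant Score points to set against 10.4.

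The face-to-face schedule in Section 14 totals 19 sessions in the experimental arm against 52 in the conventional arm. The useful conclusion is therefore that fewer visits do not cost function. When the programs are equal, the usual result will be p ≥ 0.05, and the plan does not say what that means. Reading it as similarity would reward a small or noisy trial, because non-significance becomes easier to reach as precision falls. Choosing a margin and rule after the data are seen would not repair this.

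**Working it through.** **Inputs.** From Section 6: 10.4 points, SD 12.0 (a baseline SD), 90% power, two-sided 0.05, 10% dropout, 68 patients. From Section 11: 1:1 allocation. Evaluable patients: 68 × 0.9 = 61.2, taken as 61 (30.5 per arm). Higher Constant Scores are better, so a deficit is a smaller improvement in the experimental arm.

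**1. The plan's own figure.** Normal approximation: n per arm = 2 × (1.960 + 1.282)² × 12² / 10.4² = 27.98, so 28 per arm, 56 in total, and 56 / 0.9 = 62.2, so 63 enrolled. With the t distribution: 29 per arm, 58 / 0.9 = 64.4, so 65 enrolled (66 if rounded per arm). Dividing 27.98 by the Mann-Whitney efficiency 3/π gives 29.3, so 30 per arm; 30 / 0.9 = 33.3, so 34 per arm, or 68. Section 6 names no formula, but 68 is reachable. The same arithmetic serves for detecting 10.4 points and for excluding a 10.4-point deficit when the true difference is zero, so the number 68 cannot show which was meant.

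**2. SD of the change score (assumption).** If the baseline and week-20 SDs are both 12 with correlation r, the SD of change is 12 × √(2(1 − r)): 12.0 at r = 0.5, 14.2 at r = 0.3, 17.0 at r = 0, and 9.3 at r = 0.7.

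**3. Where the two readings part.** At 30 per arm the 95% half-width is t × SD × √(2/30), with t = 2.002 on 58 df. At SD 12 this is 2.002 × 12 × 0.2582 = 6.20. An observed deficit below 6.20 is non-significant, but non-inferiority at 10.4 requires a deficit below 10.4 − 6.20 = 4.20.

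**4. How often it matters.** Steps 4 and 5 use the noncentral t with 30.5 per arm. The inconclusive rate (p ≥ 0.05, yet non-inferiority not met) is simulated with 31 and 30 patients.

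| SD | Half-width (30/arm) | Observed deficits non-significant yet failing at 10.4 | P(p ≥ 0.05), true deficit 10.4 | P(95% CI rule passes), true deficit 10.4 | P(inconclusive), true difference 0 |
|---|---|---|---|---|---|
| 12 | 6.20 | 4.20 to 6.20 | 8.6% | 2.5% | 6% |
| 14.2 | 7.34 | 3.06 to 7.34 | 19.7% | 2.5% | 17% |
| 17 | 8.79 | 1.61 to 8.79 | 34.8% | 2.5% | 32% |

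At SD 12 and a true deficit of 5.2 points (half of 10.4), p ≥ 0.05 occurs in about 62% of trials, while non-inferiority at 10.4 is met in about 38%.

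**5. Power of a proper rule.** With margin 10.4 and a true difference of zero, power is 91.4% at SD 12, 80.3% at 14.2 and 65.2% at 17. For 90% power:

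- SD 12: 29 per arm, 65 enrolled.
- SD 14.2: 41 per arm, 92 enrolled.
- SD 17: 58 per arm, 129 enrolled (130 if even).
- Margin 8 (illustrative), SD 12: 48 per arm (normal) or 49 (t), 107 or 109 enrolled.

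**The case against.** **The error rates belong to a rule the plan never states.** Section 16 does not say that p ≥ 0.05 means similar. This is correct: the 9%, 20% and 35% figures are the cost of a possible misreading. The documented fault is that the plan is silent on the result it should expect most often if its hypothesis is true.

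**The SD could be smaller than 12.** At r = 0.7 the SD of change is 9.3, the half-width at 30 per arm is 4.81, and the discordant zone disappears. A non-significant result would then hide a true 10.4-point deficit only about 1% of the time. The size of the problem therefore depends on an SD the plan does not give. At the plan's own SD of 12 it is present.

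**10.4 is plainly the intended margin.** It sits in the same section as the non-inferiority label, and the arithmetic agrees. Even so, Section 6 words it as a difference to detect, and Section 16 never uses it.

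**The documents are mixed on the objective.** Section 3 mentions only an active comparator, and Section 6 uses both kinds of wording. The authors should confirm the objective. The hypothesis and the stated sizing scenario both point to non-inferiority.

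**Per-protocol analysis is usual in non-inferiority trials.** It defines an analysis set. It does not supply a decision rule.

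**Conclusion.** The concern holds, and the plan should not go forward without correction: the primary hypothesis has no prespecified test. This follows from the text of Sections 2, 6 and 16 and depends on no assumed SD.

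The size does depend on the SD. At the plan's SD of 12, reading non-significance as similarity would pass a true 10.4-point deficit about 3.4 times as often as a proper rule (8.6% against 2.5%). The excess grows at the assumed SDs of 14.2 and 17 and vanishes at 9.3. These figures assume normal data, equal SDs in the two arms and 10% dropout. They also take 10.4 as the margin, which the documents never call it. The planned 68 patients are enough at margin 10.4 and SD 12, so the fault lies in the missing margin and decision rule.

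**What to change.** 1. **Section 6:** declare 10.4 points as the non-inferiority margin and justify it. Being the figure used for sizing is not a justification. Reconcile its source as well: Section 6 cites reference 55 for it and Section 13.1.1 cites reference 56. Reword the sample size as power to exclude a 10.4-point deficit when the true difference is zero.
2. **Section 16:** make the primary analysis the two-sided 95% confidence interval for the difference (experimental minus conventional) in change in Constant Score from baseline to week 20. Claim non-inferiority only if the lower limit is above -10.4. If it is, test superiority. State that p ≥ 0.05 in a test of difference does not show similarity.
3. **If normality is doubtful,** use an interval in Constant Score points (Hodges-Lehmann or bootstrap), not a Mann-Whitney p-value alone.
4. **Analysis set:** report the same interval in all randomised patients beside the per-protocol set.

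**Cost.** Wording in two sections and slightly more analysis. No extra patients are needed at margin 10.4 and SD 12 (about 91% power with 68; 65 would give 90%). If the SD of change is 14.2 or 17, power falls to about 80% or 65%, and 90% power needs about 92 or 129 to 130 patients. A tighter margin also costs patients: about 107 to 109 at 8 points and SD 12.

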Based on this evidence, the following outcomes will be measured:

- a) functional assessment – Constant Score
- b) patient-reported outcomes - QuickDASH

- c) range of motion of the shoulder (in degrees)

The outcome measures will be assessed pre-operatively, and then at 6, 12, 16 and 20 weeks after the surgery. In patients where a decision is made to extend the program to 24 weeks, another assessment will be made at this point.

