- i) Major medical complications occurring after surgery that prevent the discharge of the patient within 5 days after surgery
- j) Other medical and/or surgical complications that prevent the patient from complying with a rehabilitation program
- k) Blind and/or illiterate patients

10. Methods for identifying and recruiting patients

All patients admitted for rotator cuff repair during the study period will be screened for inclusion and exclusion criteria.

When a potential candidate is identified, the local investigator will approach the candidate and explain the study in detail. The prospective candidate will be given the patient information document and sufficient time to consider whether he wishes to participate in the study.

Subsequently, the prospective candidate will be given opportunity to clarify any

doubts, after which the informed consent form will be signed and dated in duplicate by the patient and the investigator. Only then will the randomization and baseline assessments be performed.

11. Patient allocation to study groups

For logistic reasons, the study will be restricted to patients living in a 20km radius around the investigation center. Patient allocation to the two groups will be performed in a random way, in a 1:1 ratio in blocks of six. This will be done using an online randomizer (<https://www.randomizer.org>).

The allocation of patients to each group will be performed centrally by one investigator - [name] - and communicated to the responsible for data acquisition only after patient enrollment. This investigator will not be involved in data collection or in outcomes assessment.

12. Blinding

The nature of the study does not allow blinding of the patients regarding study groups. However, participants will be blinded to the primary and secondary outcomes being measured. All patient assessments will be performed by an investigator blinded for randomization groups. Statistical analysis will be performed blinded for randomization group.

13. Patient assessment

Patients will be assessed pre-operatively, and then at 6, 12, 16 and 20 weeks after the surgery. In patients where a decision is made to extend the program to 24 weeks,

another assessment will be made at this point. An assessment will also be made at 12 months after surgery.

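### The supplementary 3x2 repeated-measures ANOVA has three time levels, but five common visits are scheduled to week 20 and the plan does not name the three

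*Combined protocol and SAP*

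**What the plan says.** The main comparison in section 16 of the combined protocol and SAP is a two-group test on "the change between baseline and week 20". The section then adds a second analysis: "Since outcomes will be measured in several different times during the rehabilitation program, a repeated measures analysis will also be performed", to be done "using a 3x2 ANOVA with group as an independent factor and time as a within-subjects factor". It does not list the times that make up the time factor. The general rule in the same section is "Outcome analysis will be performed using a per-protocol analysis".

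The visit schedule is in section 5: "The outcome measures will be assessed pre-operatively, and then at 6, 12, 16 and 20 weeks after the surgery". Section 13 repeats it. On week 24, section 5 says: "In patients where a decision is made to extend the program to 24 weeks, another assessment will be made at this point". Section 13 also adds a visit at 12 months.

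Section 12 states: "Statistical analysis will be performed blinded for randomization group".

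**The concern.** A two-arm trial analysed by group and time in a 3x2 layout has three time levels. The schedule gives every patient five common times to week 20, so the layout and the schedule do not match unless three visits are selected, and no selection is stated.

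This ANOVA is the only planned analysis that uses the visits between baseline and week 20. The program moves from passive to active to strengthening work over those weeks, so a difference between groups in the course of recovery could look different depending on which visits enter the model. If the three are not fixed in advance, the choice can be made once the data are in hand. Group-blinded analysis limits that risk, but it does not fix the visits.

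**Working it through.** **Inputs**
- Groups: 2, allocated 1:1 (section 11).
- Layout: 3x2 (section 16), so time has 3 levels.
- Times common to all patients up to week 20: pre-operative and weeks 6, 12, 16 and 20, which makes 5, of which 4 are post-operative (sections 5 and 13).
- Week 24: extended patients only. The heading of section 13.2 is looser about weeks 20 and 24 than the text of sections 5 and 13, but neither reading reduces the count to three.
- Patients: section 6 gives "a two-sided 0.05 significance level and a 10% dropout rate, 68 patients would be necessary".

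**The plan's own figure.** The 68 is used here only as a count. With an SD of 12.0, a difference of 10.4, two-sided 0.05 and 90% power, a t-test needs 28.97, so 29 per arm. Then 29/0.9 = 32.2, so 33 per arm and 66 in total, within two of the stated 68. Nothing below depends on that gap.

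**Data left out if the 3 is literal, per outcome, every visit attended**
- 68 patients: 5 × 68 = 340 scheduled; 3 × 68 = 204 used; 340 − 204 = 136 left out; 136/340 = 40%.
- After 10% dropout, 0.9 × 68 = 61.2, about 61 patients: 5 × 61 = 305; 3 × 61 = 183; 122 left out; 122/305 = 40%.

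The 40% is simply (5 − 3)/5. It measures unused data, not bias or lost power.

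**How many choices the plan leaves open**
- Any three of five: C(5,3) = 10.
- With the pre-operative visit: C(4,2) = 6, each losing two of the four post-operative rounds.
- Without it: C(4,3) = 4, each losing one post-operative round.
- With both the pre-operative visit and week 20: C(3,1) = 3. Each of weeks 6, 12 and 16 is missing from two of these three.

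**Effect on the group-by-time test.** With T times and N complete cases, the degrees of freedom are T − 1 and (N − 2)(T − 1). At N = 68:
- 3x2: 2 and 66 × 2 = 132.
- 5x2: 4 and 66 × 4 = 264.

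These are different tests of different hypotheses about the time course.

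**What a mixed model could add.** The plan gives no missing-data pattern, so this is one scenario. Suppose the 10% dropout is all permanent and before week 20. A five-level ANOVA, and any three-level ANOVA that includes week 20, then both keep about 61 patients. A mixed model could add partial data from at most 68 − 61 = 7 more, or from none if the per-protocol set excludes them. Scattered missed visits would favour the mixed model, because a classical ANOVA drops any patient missing one of its times.

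**The case against.** The strongest reply is that three times can be found. Weeks 6, 12 and 16 are exactly the common visits between the two times used in the main test. Weeks 12, 16 and 20 are the visits after the passive phase, which ends at week 9 in the face-to-face session schedule. Baseline, one intermediate visit and week 20 is also reasonable. This stands in part: a reader might infer that three fits no sensible set of visits, and the documents do not support that. But none of these sets is stated, and having several plausible candidates is itself the ambiguity. The first would also omit both times on which the main comparison rests.

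A reader might also infer that the intermediate visits have no usable planned analysis. That goes too far. Any three of the five times must include at least one of weeks 6, 12 and 16. If the 3 is a slip, changing one digit gives a workable 5x2 analysis. The specification is incomplete, not absent.

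It can further be said that the analysis is supplementary, that no decision rule hangs on it, and that a mixed model is more than a wrong digit requires. All three are fair. They set the weight of the point and make the one-line correction sufficient, but they do not remove the mismatch.

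**Conclusion.** The mismatch is real: three time levels against five common visits to week 20, with no three named. Whether the 3 is literal or a slip cannot be settled from the documents. If literal, 40% of scheduled assessments to week 20 are left out and one of ten visit sets must be chosen without guidance. If a slip, the layout as written is wrong.

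The counts assume 68 patients (or about 61 after the plan's own dropout) and full attendance. No effect on bias, error rate or power has been shown. A reader might infer that the trial's main result is at risk. It is not, because the baseline-to-week-20 comparison and the sample size do not use this ANOVA. The 12-month visit, which collects all three outcome measures but has no stated analysis, is a separate point and adds no weight here. This is a minor to moderate correction that should be made.

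**What to change.** **Minimum:** in section 16, change the layout to 5x2 and name the five times (pre-operative and weeks 6, 12, 16 and 20). If three times really were intended, naming and justifying them would also remove the ambiguity, but would leave two rounds unused.

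**Preferred:** replace the ANOVA with a linear mixed model on weeks 6, 12, 16 and 20, with group, visit, group-by-visit and baseline score as covariate, and a stated covariance structure. This makes baseline a covariate instead of a time level. It uses every common post-baseline visit and can keep patients with a missed visit. The gain is small, and nil if the per-protocol set excludes those patients.

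**In either case:**
- State that the repeated-measures result supports the main week-20 test and does not replace it.
- Say so if the analysis set differs from the per-protocol set.
- Report week 24 descriptively, since only extended patients have it.

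**Cost:** revised text and slightly more programming, with no new data or patients.
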